CM intervention: Through the experience and feedback from the three successful CM groups we will adapt the CBCT-Vet([name] et al., 2017) intervention for use in older adults with anxiety or depressive symptoms. This adaptation will be conducted with input from [name] and [name] (developers of CBCT® and consultants for the proposed project), and the experience and expertise of the study team. Expected adaptations include changing the focus of examples from PTSD to anxiety and depression, as well as adjustments for appropriate use with older Veterans. The CBCT-Vet includes 10 90-minute sessions that will be led by [name], a VA Staff Psychologist and Co-Investigator on the proposed project, who is certified in CBCT® with significant experience in administering CBCT-Vet. Sessions 1 - 4 assist participants in basic mindfulness breathing practices; sessions 4 - 8 focus on personal analysis of factors underlying difficulties with compassion for self or others; the final two sessions (9 and 10) review content and assist with relapse prevention. Session by session topics are: (1) Introduction and learning breathing meditation, (2) Focused attention, (3) Creating space, (4) Mindful awareness, (5) Re-engaging with heroic spirit, (6) Seeing ourselves in others, (7) Appreciation and gratitude, (8) Empathy and engaged compassion, (9) "Putting it all together," and (10) "Putting it all together 2."

Our target is to have 5-8 participants completing each 10-week intervention, thus we will enroll up to 10 per group to account for possible attrition. Two or three of the CBCT-Vet groups (depending on the degree of modification needed based on the initial group) will be conducted sequentially, such that information in the first group can be used to adapt the manualized intervention for the next group.

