Descriptive statistics will be used to summarize the variables as well as to detect outliers and data entry errors. When applicable, normality of the distribution will be examined for outcome variables and residuals of regression model with a normal probability plot. The present project is intended as a feasibility study that will inform, support, and guide development of a subsequent larger-scale VA Merit Award project. Therefore, the primary analysis will be descriptive rather than hypothesis testing. Since the interventions are delivered by group (8-10 participants per group), it is possible that measured or unmeasured characteristics of the participants in a given group or their interactions may affect psychological response to the intervention, attendance, and study outcomes. The analysis plan described below is based on no cluster effect of class. But we will assess the impact of clustering effects by fitting a random effects model for each outcome, and, if necessary, a random class effect will be included in the model to account for the correlations between the individuals in the same class. The intraclass correlation coefficient (ICC) will also be estimated to understand the correlation within class and provide advice for sample size adjustment in future studies.

Will older Veterans with psychological distress [anxiety and/or depression] enroll in and complete the proposed CM intervention? What is the completion rate? Do participants adhere to the treatment (complete practice at home)? We will assess the following outcome measures for enrollment, completion, and adherence to treatment:

- 1) $\underline{\it Enrollment\ rate}$ defined as the proportion of consented subjects among all screened and eligible patients;
- 2) Initiation rate defined as the proportion of subjects who initiate the intervention among all consented subjects;
- 3) $\underline{Completion\ rate}$ defined as the proportion of subjects who complete 6 or more sessions (out of a total of 10 sessions) of intervention among those who start the intervention;
- 4) Practice time at home defined as average minutes that subjects practice at home each week. The mean (and SD) or percentage will be calculated and the 95% confidence intervals will be estimated for all outcomes.

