The associations between patient characteristics and other clinically important baseline variables with the enrollment, completion and adherence will be assessed using univariate tests (Wilcoxon rank sum test, Kruskal-Wallis test, Fisher's exact test, or Spearman correlation coefficient).

Does CM show promise for improving well-being, symptom severity, and/or positive psychological factors relevant to successful aging? We will evaluate the improvement in depression and anxiety (BSI), social connection (SCS-R), satisfaction with life (SWLS) and positive emotions (mDES) from baseline to post-intervention using a linear random effect model and time will be included as a main effect in the model. The random effects model is suitable for examining changes in outcomes in longitudinal studies. It will include all available data, minimizing the effects of missing data on the analyses.

We will also examine the mean (and SD) change scores for each inflammatory biomarker (hs-CRP, IL-6, and TNF-), as well as the association of these changes with practice time.

Sample size assessment:

The sample size was determined based on practical consideration. Since this is a feasibility study, the goal is to examine the effect size such that it can guide future studies. We plan to enroll a total of approximately 24 to 30 participants for the CM groups (3 groups, 8-10 per group) as well as 10 participants for the healthy aging group. Sample size analyses were focused on the CM group, and performed using statistical package R.

A two-sided type I error of 0.05 was assumed.

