The sample size justification was conducted for assessing the enrollment and completion rates (primary outcomes). We assessed the precision of estimates based on projected sample size. From previous investigations, the estimated enrollment and completion rates are between 0.57 and 0.82. Therefore, we considered a range of rate from 0.60 to 0.90 and estimated the margin of error (half of the width) for the 95% confidence interval of enrollment and completion rates. The margin of error of a 95% confidence interval for a proportion is 1.96*p*(1-p)/(Square-root of n) where n is the estimated sample and p is the estimated rate. If an estimated intervention initiation rate is 0.80, a sample size of 30, 27 and 24 will produce a two-sided 95% confidence interval with a margin of error of 0.058, 0.071 and 0.064, respectively. For an estimated completion rate of 0.60, a sample size of 30, 27 and 24 will produce a two-sided 95% confidence interval with a margin of error of 0.086, 0.091 and 0.096, respectively.

We assessed the power for detecting a significant change in psychological outcomes. With a sample size of 24, 27 and 30, we will have 80% power to detect an effect size of 0.53, 0.56 and 0.60 for the change in outcomes from baseline to post-intervention. These effect sizes are achievable based on previous studies, where we observed an effect size of 0.5 for PHQ-9 (mean = 2.3, SD = 4.6), 0.65 for SCS-R (mean = 6.4, SD = 9.9), 1.4 for SWLS (mean = 9.0, SD = 6.6), 0.53 for mDES positive emotion (mean = 4.8, SD = 9.1), and 5.35 for mDES negative emotions (mean = 7.5, SD = 1.4).

Women and ethnic minorities: Women and ethnic minorities will be included in proportion to their representation of Veterans in the VASDHS and PCMHI program. This proportional sampling plan fosters both feasibility of the study and overall generalizability of findings. We recognize that the issues of anxiety and depression among women Veterans is exceptionally important, but warrants separate studies designed and focused specifically to address the issues of most salience to women Veterans.

Children: No children will be included as the scientific focus of this project is on older Veterans

Temporary COVID-19 Updates*

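### The completion margin is computed on Veterans enrolled rather than Veterans who start, and no margin is given for enrollment, the other primary outcome

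*Combined protocol and SAP*

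**What the plan says.** The Analytic plan in Section 9 gives each feasibility rate its own denominator. Enrollment is the share of screened and eligible patients who consent. Initiation is the share of consented subjects who begin. Completion is attendance at 6 or more of the 10 sessions, as a share "of intervention among those who start the intervention".

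The Sample size assessment fixes the planned number: "We plan to enroll a total of approximately 24 to 30 participants for the CM groups (3 groups, 8-10 per group"). The CM intervention text shows that this is a count before losses: "thus we will enroll up to 10 per group to account for possible attrition".

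On precision, the Sample size assessment says: "The sample size justification was conducted for assessing the enrollment and completion rates (primary outcomes"). It reports that margins were worked out for both of those rates, over values from 0.60 to 0.90. Two sets of margins are then printed. The first begins "If an estimated intervention initiation rate is 0.80" and gives 0.058, 0.071 and 0.064 for n of 30, 27 and 24. The second reads "For an estimated completion rate of 0.60, a sample size of 30, 27 and 24 will produce" margins of 0.086, 0.091 and 0.096. No enrollment margin follows. No expected number of eligible Veterans or of starters is given anywhere.

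**The concern.** The completion margins use every enrolled Veteran, while the plan's own definition leaves out those who never start. Because the preceding sentence allows for one in five not starting, the two sentences cannot share the same n. Separately, one of the two primary outcomes has no precision figure, and a rate not named as primary has one.

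Feasibility rates are the main product of this study and are meant to guide a larger randomised trial. Its planners will use the enrollment rate to decide how many eligible Veterans must be found, and the completion rate to allow for attrition. They need to know how precisely each will be estimated. As written, the plan is optimistic about one and silent about the other.

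**Working it through.** **Inputs**

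- Two-sided 95% interval, z = 1.96: "A two-sided type I error of 0.05 was assumed" (Sample size assessment).
- Enrolled in the CM groups: 24, 27 or 30 (Sample size assessment).
- Illustrative initiation rate 0.80 and completion rate 0.60; range considered for enrollment and completion 0.60 to 0.90 (Sample size assessment).
- Denominators: as defined in the Analytic plan.
- Assumptions, because the documents give no counts: starters = enrolled × initiation rate; eligible = CM consents ÷ enrollment rate, with 24 to 30 CM consents.

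**Step 1. Reproduce the printed completion margins.** The printed formula is 1.96 × p × (1 − p) / √n. At p = 0.60:

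- n = 30: 1.96 × 0.24 / √30 = 0.0859 (printed 0.086)
- n = 27: 1.96 × 0.24 / √27 = 0.0905 (printed 0.091)
- n = 24: 1.96 × 0.24 / √24 = 0.0960 (printed 0.096)

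The figures match, so all 30, 27 or 24 enrolled Veterans are in the denominator. For initiation at 0.80 the same formula gives 0.0573, 0.0604 and 0.0640. The printed 0.071 at n = 27 does not reproduce.

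The printed formula has p(1 − p) outside the square root. The standard form is 1.96 × √(p(1 − p)/n). That is a separate error; both forms are shown below so that the effect of the denominator can be seen by itself.

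**Step 2. Put completion on starters, at initiation 0.80, p = 0.60.**

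| Enrolled | Expected starters | Printed formula: enrolled → starters | Standard formula: enrolled → starters |
|---|---|---|---|
| 24 | 24 × 0.80 = 19.2 | 0.096 → 0.107 | 0.196 → 0.219 |
| 27 | 27 × 0.80 = 21.6 | 0.091 → 0.101 | 0.185 → 0.207 |
| 30 | 30 × 0.80 = 24.0 | 0.086 → 0.096 | 0.175 → 0.196 |

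Under either formula the margin grows by 1/√0.80 = 1.12. Correcting the formula alone would therefore leave this error in place.

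**Step 3. Vary the initiation rate.** Applying 0.60 to 0.90 to initiation is an assumption.

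- Initiation 0.60 with 24 enrolled: 14.4 starters, margin 1.96 × √(0.24/14.4) = 0.253.
- Initiation 0.90 with 30 enrolled: 27 starters, margin 1.96 × √(0.24/27) = 0.185.

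**Step 4. Compute the missing enrollment margin (standard formula).**

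| Enrollment rate | Eligible, for 24 to 30 consents | Margin |
|---|---|---|
| 0.60 | 40 to 50 | 0.152 to 0.136 |
| 0.80 | 30 to 37.5 | 0.143 to 0.128 |
| 0.90 | 26.7 to 33.3 | 0.114 to 0.102 |

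Here 24 to 30 is the numerator of the rate. The denominator is larger, so the shift goes the opposite way from the shift for completion.

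**The case against.** The strongest reply is that little turns on this. The completion margin widens by only about 2 percentage points, and the corrected figure at 30 enrolled (0.196) equals the uncorrected figure at 24. The missing enrollment margin would be narrower than one computed at 24 to 30. The formula error in the same sentences is far larger: at p = 0.60 and n = 30 it prints 0.086 where the standard form gives 0.175. The primary analysis is descriptive, the plan sets no threshold on either rate, and 95% intervals will be reported for all the rates when data are in. All of this stands. It limits the size of the point without removing it: the completion figure is on a denominator that the plan's own definition rules out, and the promised enrollment figure is absent. Reading initiation as a slip for enrollment does not help, since 24 to 30 would then be the numerator.

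Three stronger readings are tempting, and the documents do not support them.

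- A reader might infer that the wrong n was used for every rate. For initiation, the number consented is the correct denominator, and no enrollment margin exists to be wrong.
- A reader might infer that the sample size rests on precision alone. The Sample size assessment says that the number was set on practical grounds and adds a power statement for change in psychological outcomes.
- A reader might multiply the two printed rates, 0.80 × 0.60 = 0.48, expect 3.8 to 4.8 completers per class of 8 to 10, and see a conflict with "Our target is to have 5-8 participants completing each 10-week intervention". The two rates are separate illustrations and are never offered as a joint scenario. Within the range considered, 0.80 × 0.80 = 0.64 gives 5.1 to 6.4 completers, which meets the target.

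**Conclusion.** The point holds as a modest but definite correction that should be made. The completion margins are computed on 24 to 30 enrolled when the definition calls for starters. At the illustrative initiation rate of 0.80 the correct margins are about 12% wider: 0.219/0.207/0.196 for 24/27/30 enrolled with the standard formula at a completion rate of 0.60. The enrollment margin, for a primary outcome, is missing. On CM consents it would be about 0.10 to 0.15 for rates of 0.60 to 0.90.

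The completion figures depend on the assumed initiation rate, and the enrollment figures on an eligible count inferred from consents. If the 10 healthy aging consents are also counted (34 to 40 in all), a rate of 0.60 implies 57 to 67 eligible and a margin of 0.128 to 0.118. All the figures treat Veterans as independent. The planned number, the completer target and the eventual analysis of the rates are unaffected.

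**What to change.** Rewrite the precision paragraph of the Sample size assessment by rate, in the same edit that corrects the margin formula:

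- **Enrollment:** denominator is the expected number screened and eligible. State that number as an assumption, and whether it covers CM recruitment only. For 24 to 30 CM consents: 40 to 50 eligible and margin 0.152 to 0.136 at a rate of 0.60; about 27 to 33 eligible and margin 0.114 to 0.102 at 0.90.
- **Initiation:** denominator is the 24, 27 or 30 consented. At 0.80 the standard formula gives 0.160, 0.151 and 0.143.
- **Completion:** denominator is expected starters, with the assumed initiation rate or range stated. At initiation 0.80 and completion 0.60: 0.219, 0.207 and 0.196 for 24, 27 and 30 enrolled; over initiation 0.60 to 0.90, 14 to 27 starters and margins of 0.253 to 0.185.

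The target of 5 to 8 completers per class needs no change on this account. The cost is a few lines of text, with no change to design or numbers recruited. The only downside is that the stated completion precision becomes slightly less favourable.

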Psychoeducational healthy aging group: As part of this project, we will develop and test a 10-week psychoeducational group focused on topics in healthy aging to examine its feasibility as a control condition for a subsequent VA Merit-supported randomized controlled trial. [name], in addition to his VA position and roles, is an active member of the Center for Healthy Aging at UC San Diego. The Center for Healthy Aging has multiple resources for community education regarding healthy aging, including a library of videotaped community-focused talks, such as increasing happiness, mental resilience and health, nutrition, and physical activity. We will incorporate these videos as part of 90-minute sessions wherein the key information from talks is shown to participants, with a follow-up discussion and review period led by the group facilitator. In the context of the present feasibility study, we anticipate modifying and refining the content and format of the group in response to participant feedback.

Process and outcome measures: As a feasibility study, we will not be testing hypotheses regarding the efficacy of CBCT-Vet in reducing psychological distress with inferential statistics. However, in order to support our planned subsequent VA Merit application, we will be examining descriptive statistics of observed patterns and estimated effect sizes of change on key measures described below.

Baseline and post-intervention: Each participant will meet individually with a trained Research Assistant (RA; To Be Named (TBN)) for two 90-minute assessment sessions (baseline and post-intervention). The final assessment will be scheduled within 2-weeks of the participant's final intervention group session. Measures will include:

Psychological distress: Brief Symptom Inventory-18 (BSI; depression, anxiety, and somatization) (Boulet & Boss, 1991).

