Compassion, empathy, mindfulness, and social connectedness: As a feasibility study, we will use a larger array of measures than we anticipate employing in a subsequent VA Merit-supported RCT. Although we have prior experience with each of these measures in other contexts, their use in this feasibility study will enable us to more comprehensively identify those with most potential and which are most appropriate for this population. Measures will include: Self-Compassion Scale – Short Form, Toronto Empathy Questionnaire, Cognitive and Affective Mindfulness Scale – Revised, Social Connectedness Scale - Revised and the UCLA Loneliness Scale - Third Edition.

Well-being/Quality of Life: Physical and mental composite scores from the 12-item Short Form Health Survey (SF-12) and Satisfaction with Life Scale.

General positive psychological factors: 10-item version of the Connor-Davidson Resilience Scale , Life Orientation Test – Revised (a measure of optimism) , San Diego Wisdom Scale (SD-WISE)) and Center for Epidemiological Studies – Depression Scale (CES-D; happiness factor).

Biomarkers: At the baseline and final visits, approximately 15 mL (2-3 teaspoons) of blood will be drawn from each participant by the VA Clinical Laboratory via standard blood draw. Three inflammatory markers will be assayed: high sensitivity C-reactive protein (hs-CRP), interleukin-6 (IL-6), and tumor necrosis factor-alpha (TNF-). Assays will be conducted using standardized methods through the VASDHS 6th floor research laboratory of Co-I [name].

Additional final visit measures: Participants will complete the modified Differential Emotions Scale (mDES) (Fredrickson et al., 2003) at each weekly session to assess changes in positive emotion during the course

of treatment. Credibility of the interventions will be assessed at the final visit with a 3-item measure adapted from Borkovec & Nau (1972) and the Client Satisfaction Questionnaire (Attkisson & Greenfield, 1994) as well as via post-intervention interviews.

Analytic plan:

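### The effect sizes said to be detectable with 80% power are listed in reverse order against the sample sizes: 24, 27 and 30 should pair with 0.60, 0.56 and 0.53

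*Combined protocol and SAP*

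**What the plan says.** The sample size assessment in Section 9 sets a two-sided type I error of 0.05, restricts the calculation to the CM participants, and plans "approximately 24 to 30 participants for the CM groups (3 groups, 8-10 per group"). For the change in outcomes from baseline to post-intervention it then says: "With a sample size of 24, 27 and 30, we will have 80% power to detect an effect size of 0.53, 0.56 and 0.60".

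The next sentence justifies those effects: "These effect sizes are achievable based on previous studies, where we observed an effect size of 0.5 for PHQ-9" (mean 2.3, SD 4.6). It goes on to cite 0.65 for SCS-R (6.4, SD 9.9), 1.4 for SWLS (9.0, SD 6.6), 0.53 for mDES positive emotion (4.8, SD 9.1) and 5.35 for mDES negative emotions (7.5, SD 1.4).

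The outcomes to be modelled are named in the Analytic plan: "We will evaluate the improvement in depression and anxiety (BSI), social connection (SCS-R), satisfaction with life (SWLS) and positive emotions (mDES"). On clustering, the same part says: "The analysis plan described below is based on no cluster effect of class".

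**The concern.** With alpha and power fixed, a larger sample detects a smaller effect. The printed list runs the other way: the detectable effect rises from 0.53 to 0.60 as the sample rises from 24 to 30. No test behaves like that, so at least two of the three pairings must be wrong.

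Two things depend on it. The sentence overstates power at the bottom of the planned range and understates it at the top, and a reader planning the follow-up trial could carry the wrong pairing forward. The claim that the effects are achievable also rests on comparing past effects with this list, so each past effect should be checked against the correct order.

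**Working it through.** **Inputs.** Two-sided alpha 0.05, power 80%, n = 24, 27 and 30, and a within-person baseline-to-post contrast (Section 9, Sample size assessment). No clustering (Section 9, Analytic plan). The plan does not name the test behind the figures; a paired t-test on change scores is inferred and checked below.

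**Formula.** With d = mean change / SD of change, the test statistic follows a noncentral t distribution with n − 1 degrees of freedom and noncentrality d√n. Power is the probability that it falls beyond the two-sided 5% critical value.

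**Reproducing the plan's figures.** Solving for d at 80% power, and computing power at the printed pairs:

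| n | Printed d | Power at printed d | d at 80% power |
|---|---|---|---|
| 24 | 0.53 | 70.1% | 0.597 |
| 27 | 0.56 | 80.0% | 0.560 |
| 30 | 0.60 | 88.8% | 0.529 |

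To two decimals, the last column is 0.60, 0.56 and 0.53: the plan's values with the outer two exchanged.

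A hand check agrees. Equal power needs roughly equal d√n. As printed, d√n is 0.53 × 4.899 = 2.60, 0.56 × 5.196 = 2.91 and 0.60 × 5.477 = 3.29. With the list reversed it is 0.60 × 4.899 = 2.94, 0.56 × 5.196 = 2.91 and 0.53 × 5.477 = 2.90.

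**Other tests.** None gives the printed order, and none gives the same three values. At n = 24, 27 and 30:
- normal approximation: 0.572, 0.539, 0.511
- one-sided t: 0.523, 0.491, 0.465
- one-sided normal: 0.508, 0.479, 0.454
- independent two-sample t with n per arm: 0.826, 0.777, 0.736

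**The cited effects against the corrected list.** The ratios follow from the plan's own means and SDs:

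| Outcome | Effect | Power at 24 / 27 / 30 | Modelled? |
|---|---|---|---|
| PHQ-9 | 2.3/4.6 = 0.500 | 65% / 71% / 75% | no |
| mDES positive | 4.8/9.1 = 0.527 | 70% / 75% / 80% | yes |
| SCS-R | 6.4/9.9 = 0.646 | 86% / 90% / 93% | yes |
| SWLS | 9.0/6.6 = 1.364 | over 99% at each | yes |
| BSI | none given | cannot be computed | yes |

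The mDES row is a two-point simplification, since mDES is collected "at each weekly session to assess changes in positive emotion". The mDES negative figure is left aside because that outcome is not among those modelled.

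**Dependence on follow-up.** The values 24 to 30 are enrolment numbers. The CM intervention text in Section 9 targets 5 to 8 completers per group, which is 3 × 5 = 15 to 3 × 8 = 24 over three groups. Completing the sessions is not the same as being assessed, so the number with both measurements is unknown. As an illustration, if 60% of 30 were assessed (18 people), the detectable effect would be 0.70 and power for the SCS-R effect 73%.

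**The case against.** The strongest defence is that little hangs on this sentence. The sample size is said to rest on practical considerations, the primary outcomes are rates, and the plan states that "the primary analysis will be descriptive rather than hypothesis testing" and that "we will not be testing hypotheses regarding the efficacy of CBCT-Vet in reducing psychological distress with inferential statistics". That stands, and it keeps the point minor. It does not make the sentence true, and nothing elsewhere in the document corrects it.

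It can also be said that the power sentence lacks the word 'respectively', so the pairing is only implied. Pairing in order is still the natural reading. The margin-of-error sentences just before it list the sample sizes as 30, 27, 24, so it may be the list of n that was turned round. The correction is the same either way.

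A reader might infer that the achievability claim has no support at all for symptoms, or that the trial is too small because an effect of 0.50 would need 34 people for 80% power. The document does not support either reading. PHQ-9 at 0.50 is close to 0.53 and has 75% power at 30. PHQ-9 is not a modelled outcome, so a sample size for it has little planning relevance. The Section 7 background on compassion meditation also cites a meta-analysis with moderate improvements in anxiety and depression, although it gives no BSI figure. And the achievability sentence says that effects of this size have been seen before; it does not promise 80% power for each outcome at each sample size.

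A reader might also fold in the differing CM enrolment figures (20 to 30 in Section 5, two or three groups under CM intervention in Section 9, 24 to 30 in three groups in the sample size assessment). That is a separate matter and no part of the error in the power sentence.

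**Conclusion.** The power sentence is wrong as written. The three effect sizes are the right set in the wrong order: 0.60 at 24, 0.56 at 27 and 0.53 at 30. At the printed pairings, power is 70%, 80% and 89% instead of 80% throughout. That the order is impossible needs no assumption about the test. The corrected values rest on a two-sided 0.05 paired t-test, no class clustering and complete pre-post data; the exact match to the plan's three numbers makes that test very likely the one used.

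The achievability claim holds in part. It is supported for SCS-R and SWLS at 24 to 30 if follow-up is complete, and for mDES positive only at about 30. The one depression-scale effect cited falls slightly short of all three values, and BSI has no effect size to compare. Severity is minor.

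**What to change.** Replace the power sentence with wording such as:

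> With 24, 27 and 30 CM participants who have both baseline and post-intervention data, and assuming no class clustering, a two-sided 0.05 paired t-test has 80% power to detect effect sizes of 0.60, 0.56 and 0.53, respectively.

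Add that these numbers equal the enrolment target and so assume that everyone enrolled is followed up, with an illustration of what a shortfall does (18 assessed gives 0.70).

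Qualify the achievability sentence outcome by outcome, along the lines of the verdict, and either supply a BSI effect size with its source or say that none is available.

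This is a text correction only. It adds no participants and leaves the outcomes, analysis and design unchanged. The stated detectable effect becomes less favourable at 24 (0.60 instead of 0.53) and more favourable at 30 (0.53 instead of 0.60).
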